			Single-Blin	d Placeb	o Run-in	Double-Blind Treatment Period					Per	iod		
Study Day or Week:	Screening Visit (a)	D -21 (b) or D -28 (c)	D -14 (d,e)	D -7	D -1 (v)	D1	W2	W4	W6	Final clinic/ ET W8 (f)	ABPM Removal Visit (w)	Tele- phone Follow- up (g)		
Visit Window	N/A	N/A	N/A	N/A	N/A	N/A	±2d	±2d	±2d	±2d	N/A	N/A		
Visit Number:	1	N/A	2	3	4	5	6	7	8	9	10	N/A		
Informed consent	X													
Inclusion/exclusion criteria	X		X	X	X	X								
Demographics and medical history	X													
Medication history	X													
Physical examination	X					X				X				
PTE assessment (h)	X		X											
AE assessment (i,j,r)			X	X	X	X	X	X	X	X	X	X		
Vital signs (k)	X		X	X	X	X	X	X	X	X	X			
Weight, height, and BMI (l)	X					X	X	X	X	X	X			
12-lead ECG	X					X				X				
Clinical laboratory tests (m)	X					X	X	X		X				
Urine albumin and creatinine and UACR (n)						X				X				
HbA1c	X					X				X				
Estimated GFR (n)	X					X	X	X		X				
Serum hCG (o)	X		X			X		X		X				
Urine pregnancy test (o,p)						X								
Guidance on avoidance of pregnancy, ova donation, and acceptable methods of contraception	X		X	X	X	X	X	X	X	X	X	X		
Notify subject to begin washout period (q)		X												
Plasma renin concentration and activity, plasma and urine aldosterone						X		X		X				
ABPM start (subgroup only)					X					X				
ABPM removal (subgroup only)						X					X			

CONFIDENTIAL

		Washout Single-Blind Placebo Run-in				D	l. l. Di	Post-Treatment Period				
Study Day or Week: Visit Window	Screening Visit (a)	D -21 (b) or D -28 (c) N/A	D -14 (d,e)	D -7 N/A	D -1 (v)	D1 N/A	w2 ±2d	W4 ±2d	W6	Final clinic/ ET W8 (f) ±2d	ABPM Removal Visit (w)	Tele- phone Follow- up (g) N/A
Visit Number:	1	N/A	2	3	4	5	6	7	8	9	10	N/A
Concurrent medical conditions (r)	X											
Concomitant medications	X		X	X	X	X	X	X	X	X	X	X
Access IVRS/IWRS (s)	X		X			X	X	X	X	X		
Dispense single-blind study placebo for run-in and dose in-clinic (t)			X									
Redispense single-blind placebo for run-in				X								
Last dose of single-blind placebo (u)					X							
Dispense double blind study drug						X	X	X	X			
Last dose of double blind study drug										X		
Clinic dosing (u)			X	X	X	X	X	X	X	X		
Compliance assessment				X	X	X	X	X	X	X		

Footnotes for Appendix A are on the next page.

Footnotes for Appendix A

D=Day, W=Week.

- (a) The Screening Visit should be scheduled before the washout/run-in period begins so that laboratory tests results can be reviewed and subject eligibility can be confirmed before other treatments are stopped or placebo is initiated.
- (b) Subjects taking previous antihypertensive agents are required to participate in a 3-week washout period (Days -21 to -1).
- (c) If the subject's previous antihypertensive treatment includes amlodipine or chlorthalidone, then the washout must be extended to 4 weeks (Days -28 to -1).
- (d) Subjects who have not received antihypertensive treatment within 28 days before screening can be entered into the run-in period as soon as all inclusion and exclusion criteria, including laboratory results, have been verified.
- (e) At minimum, the run-in should be 10 days but can extend to as long as the subject has an adequate supply of single-blind placebo run-in study medication.
- (f) Conduct Final Visit procedures for subjects who are randomized and discontinued early per Section 7.6.
- (g) Telephone contact for the follow-up AE and concomitant medication assessments should be made approximately 14 days after the last dose (single-blind placebo or double-blind).
- (h) Reports of pretreatment events should be solicited at each visit from the time that informed consent is acquired until the first dose of placebo run-in study medication.
- (i)AEs should be solicited at each visit from the time that single-blind placebo run-in study medication is started through 14 days after the last dose (via the telephone follow-up AE assessment).
- (j) Spontaneous reports of AEs and SAEs should be collected from the time of the first dose of single-blind placebo run-in medication through 14 or 30 days, respectively, after the last dose.
- (k) Includes sitting and standing BP and pulse rate. Pulse rate will be taken manually while sitting and standing.
- (1) Collect height at the Screening (Visit 1) only; BMI will be calculated during data analysis at Screening (Visit 1).
- (m) Hematology, serum chemistry, and urinalysis tests (as listed in Table 9.a). After informed consent is provided, subjects will be asked to fast prior to blood draws within the Screening Period, and will be instructed to fast for at least 8 hours prior to blood draws on Day 1 (Visit 5), Week 2 (Visit 6), Week 4 (Visit 7), and Week 8/ET (Visit 9).
- (n) UACR and estimated GFR will be calculated by the central laboratory.
- (o) Women of childbearing potential only.
- (p) Urine pregnancy test is performed at the site and must be negative for subject prior to randomization on Day 1 (Visit 5).
- (q) Subject can be notified by telephone to begin the washout period.
- (r) Data on medical conditions that require Continuous Positive Airway Pressure (CPAP) will be collected during the study. If CPAP is ongoing at the time of informed consent, the medical condition that required CPAP will be captured on the concurrent medical conditions (e)CRF. If CPAP is administered after first dose of study drug, then the medical condition will be captured as an AE.
- (s) If a subject withdraws early, contact IVRS/IWRS to document the ET.
- (t) Subjects to take the first dose of single-blind placebo run-in study medication in-clinic.
- (u) Instruct subjects to withhold their dose of study drug, if applicable so they can be dosed in-clinic. For ABPM subgroup subjects, clinic dosing at 8:00 AM (±2 hours) for Visits 4 and 9.
- (v) Visit 4 is only applied to ABPM subgroup subjects; if the ABPM measurement does not pass the predefined criteria (fails), the subject must continue the current treatment and ABPM should be repeated within 3 days.
- (w) Visit 10 is only applied to ABPM subgroup subjects; if the ABPM measurement does not pass the predefined criteria (fails), the subject must continue the current treatment and ABPM should be repeated within 3 days.

Rationale for Amendment

To add clinical laboratory tests (clinical chemistry, hematology, and urinalysis) and eGFR at Week 2 (Visit 6) to be consistent with the current Takeda standard. Week 2 blood draw will allow full characterization of possible early postdose laboratory parameter changes that are considered relevant for monitoring with use of an ARB class of drug, including serum creatinine, electrolytes, liver enzyme tests, CPK, and hemoglobin. Mild ALT and AST elevations above ULN (but not exceeding 3×ULN) were observed in 7 of 16 subjects on Day 11 of a phase 1 study of TAK-491 in healthy Chinese subjects.

To add a serum pregnancy test at Day -14 (Visit 2), remove urine pregnancy tests from Day -7 (Visit 3) and Week 4 (Visit 7), and add guidance on avoidance of pregnancy and ova donation to Visit 10 to be consistent with the current Takeda standard. Footnote (r) modified for clarity.

#### 2.0 LIST OF ABBREVIATIONS

ABPM ambulatory blood pressure monitoring

AE adverse event

ANCOVA analysis of covariance
ANOVA analysis of variance
BMI body mass index
CI confidence interval
DBP diastolic blood pressure
ECG electrocardiogram

eCRF electronic case report form

eGFR estimated glomerular filtration rate

FAS full analysis set

ICH International Conference on Harmonization

LLN lower limit of normal

LOCF last observation carried forward MAV markedly abnormal values

MedDRA Medical Dictionary for Regulatory Activities

MI multiple imputation OC observed case

PE physical examination
PPS per protocol set
PT preferred term
QD once daily

SAP statistical analysis plan
SBP systolic blood pressure
SD standard deviation
SE standard error

SI system International SOC system organ class

TEAE treatment-emergent adverse event

ULN upper limit of normal

WHO World Health Organization

#### 3.0 INTRODUCTION

This statistical analysis plan (SAP) describes the planned statistical analyses and data presentations for TAK-391\_305, a phase 3, double-blind, randomized, parallel-group study to evaluate the efficacy and safety of TAK-491 compared with valsartan over an 8 week treatment period in Chinese subjects with essential hypertension (mean sitting clinic systolic blood pressure (SBP)  $\geq$  150 and  $\leq$  180 mm Hg on Day 1).

The purpose of this document is to ensure the credibility of the study findings by specifying the statistical approaches to the analysis of the double-blind data prior to database lock. This SAP was developed based on the International Conference on Harmonization (ICH) E3 and E9 Guidelines and in reference to the following document:

• Protocol TAK-491\_305 Amendment No.4 dated 09 May 2016.

Any deviations during the analysis and reporting process from the current SAP will be described and justified in the final report. Analysis issues that suggest changes to the principal features stated in the protocol will be documented in a protocol amendment. Otherwise, the statistical analysis plan will be updated through an amendment with the changes in the analysis documented in the amendment.

#### 4.0 OBJECTIVES

## 4.1 Primary Objective

The primary objective of this study is to evaluate the antihypertensive effect of TAK-491 compared with valsartan in Chinese subjects with essential hypertension.

## 4.2 Secondary Objective

The secondary objective is to evaluate the safety and tolerability of TAK-491 compared with valsartan.

## 4.3 Study Design

This is a phase 3, multicenter, randomized, double-blind, parallel-group study to evaluate the efficacy and safety of TAK-491 compared with valsartan over an 8 week treatment period in Chinese subjects with essential hypertension (mean sitting clinic SBP ≥150 and ≤180 mm Hg on Day 1). A subgroup of approximately 60 subjects/arm from selected sites will undergo 24-hour ambulatory blood pressure monitoring (ABPM) 2 times during the study.

This study will be conducted in China at approximately 20 to 25 sites and will include approximately 600 randomized subjects.

Before initiation of treatment, all subjects will participate in a 2-week, single-blind, placebo runin period (Days -14 to -1). Subjects who have not received antihypertensive treatment within 28 days before screening can be entered into the run-in period as soon as all inclusion and exclusion criteria, including laboratory results, have been verified. Subjects taking previous antihypertensive agents will be required to participate in a 3-week washout/placebo run-in period (Days -21 to -1). If the subject's previous antihypertensive treatment includes amlodipine or chlorthalidone, then the washout/placebo run-in must be extended to 4 weeks (Days -28 to -1). Screening (Visit 1) will be scheduled before the washout/run-in period begins so that laboratory test results can be reviewed and subject eligibility can be confirmed before other treatments are stopped or placebo is initiated. At Day -14 (Visit 2), subjects will receive the first dose of single-blind placebo in clinic.

[figure not shown]
At Day 1 (Visit 5), eligible subjects will be randomly assigned to one of the following 3 groups with a 1:1:1 ratio:

- TAK-491 40 mg QD.
- TAK-491 80 mg QD.
- Valsartan 160 mg QD.

Subjects will be given the first dose of randomized study drug in the clinic at Day 1 (Visit 5). The last dose of randomized study drug will be taken the day of Week 8 visit (Visit 9). End of study assessment will be taken at Week 8/Early Termination (Visit 9). All subjects who receive study drug (placebo or double-blind) will be required to have a follow-up telephone call at approximately 14 days after the last dose.

A schematic of the study design is included as Figure 4.a. A schedule of assessments is listed in Table 4.a.

Figure 4.a Schematic of Study Design

V=visit, N/A=not applicable, D=day, HTN=hypertension, Wk=week, ET=Early Termination.

- (a) The Screening Visit should be scheduled before the washout/run-in period begins so that laboratory tests results can be reviewed and subject eligibility can be confirmed before other treatments are stopped or placebo is initiated.
- (b) Subjects may be notified by telephone to begin the washout period.
- (c) Subjects taking previous antihypertensive agents are required to participate in a 3-week washout/run-in period (Days -21 to -1).
- (d) If the subject's previous antihypertensive treatment includes amlodipine or chlorthalidone, then the washout must be extended to 4 weeks (Days -28 to -1).
- (e) The first dose of placebo will be taken at the clinic on Day -14 (Visit 2).
- (f) Subjects who have not received antihypertensive treatment within 28 days prior to Screening can be entered into the run-in period as soon as all inclusion and exclusion criteria, including laboratory results, have been verified.
- (g) Last dose of double-blind is the day of Week 8/Final clinic visit or ET (Visit 9). And, in subgroup of ABPM subjects will start 24-hour ABPM measurement.
- (h) The follow-up telephone contact should be made approximately 14 days after the last dose.
- (i) Visit 4 only applies to ABPM subgroup subjects; start 24-hour ABPM measurement.
- (j) Visit 10 only applies to ABPM subgroup subjects.

 Table 4.a
 Schedule of Study Procedures

			Wash	out								
			Si	ngle-B		Dov	ıbla Bli	nd Tro	atmon	t Period		reatment eriod
Study Day:	Screen- ing Visit (a)	D -21 (b) or D -28 (c)	D -14 (d,e)	D -7	D -1 (v)	D00	W2	W4	W6	Final clinic/ET W8	ABPM Removal Visit (w)	Telephone Follow- up
Visit Windows	N/A	N/A	N/A	N/A	N/A	N/A	±2d	±2d	±2d	±2d	N/A	N/A
Visit Number:	1	N/A	2	3	4	5	6	7	8	9	10	N/A
Informed consent	X											
Inclusion/exclusion criteria	X		X	X	X	X						
Demographics and medical history	X											
Medication history	X											
Physical examination	X					X				X		
PTE assessment (h)	X		X									
AE assessment (i,j,r)			X	X	X	X	X	X	X	X	X	X
Vital signs (k)	X		X	X	X	X	X	X	X	X	X	
Weight, height, and BMI (1)	X					X	X	X	X	X	X	
12-lead ECG	X					X				X		
Clinical laboratory tests (m)	X					X	X	X		X		
Urine albumin and creatinine and UACR (n)						X				X		
HbA1c	X					X				X		
Estimated GFR (n)	X					X	X	X		X		
Serum hCG (o)	X		X			X	- 1	X		X		
Urine pregnancy test (o,p)	71		1			X		1		71		
Guidance on avoidance of pregnancy, ova donation, and acceptable methods of contraception	X		X	X	X	X	X	X	X	X	X	X
Notify subject to begin washout period (q)		X										
Plasma renin concentration and activity, plasma and urine aldosterone						X		X		X		
ABPM start (subgroup only)					X					X		
ABPM removal (subgroup only)						X					X	
Concurrent medical conditions (r)	X											
Concomitant medications	X		X	X	X	X	X	X	X	X	X	X
Access IVRS/IWRS (s)	X		X			X	X	X	X	X		
Dispense single-blind study placebo for run-in and dose in- clinic (t)			X									
Redispense single-blind placebo for run-in				X								
Last dose of single-blind placebo (u)					X							
Dispense double blind study drug						X	X	X	X			
Last dose of double blind study drug										X		
Clinic dosing (u)			X	X	X	X	X	X	X	X		
Compliance assessment				X	X	X	X	X	X	X		

Footnotes for Table 5.a are on the next page.

D=Day, W=Week.

- (a) The Screening Visit should be scheduled before the washout/run-in period begins so that laboratory tests results can be reviewed and subject eligibility can be confirmed before other treatments are stopped or placebo is initiated.
- (b) Subjects taking previous antihypertensive agents are required to participate in a 3-week washout period (Days 21 to -1).
- (c) If the subject's previous antihypertensive treatment includes amlodipine or chlorthalidone, then the washout must be extended to 4 weeks (Days -28 to -1).
- (d) Subjects who have not received antihypertensive treatment within 28 days before screening can be entered into the run-in period as soon as all inclusion and exclusion criteria, including laboratory results, have been verified.
- (e) At minimum, the run-in should be 10 days but can extend to as long as the subject has an adequate supply of single-blind placebo run-in study medication.
- (f) Conduct Final Visit procedures for subjects who are randomized and discontinued early per protocol Section 7.6
- (g) Telephone contact for the follow-up AE and concomitant medication assessments should be made approximately 14 days after the last dose (single-blind placebo or double-blind).
- (h) Reports of pretreatment events should be solicited at each visit from the time that informed consent is acquired until the first dose of placebo run-in study medication.
- (i) AEs should be solicited at each visit from the time that single-blind placebo run-in study medication is started through 14 days after the last dose (via the telephone follow-up AE assessment).
- (j) Spontaneous reports of AEs and SAEs should be collected from the time of the first dose of single-blind placebo run-in medication through 14 or 30 days, respectively, after the last dose.
- (k) Includes sitting and standing BP and pulse rate. Pulse rate will be taken manually while sitting and standing.
- (l) Collect height at the Screening (Visit 1) only; BMI will be calculated during data analysis at Screening (Visit 1).
- (m) Hematology, serum chemistry, and urinalysis tests. After informed consent is provided, subjects will be asked to fast prior to blood draws within the Screening Period, and will be instructed to fast for at least 8 hours prior to blood draws on Day 1 (Visit 5), Week 2 (Visit 6), Week 4 (Visit 7), and Week 8/ET (Visit 9).
- (n) UACR and estimated GFR will be calculated by the central laboratory.
- (o) Women of childbearing potential only.
- (p) Urine pregnancy test is performed at the site and must be negative for subject prior to randomization on Day 1 (Visit 5).
- (g) Subject can be notified by telephone to begin the washout period.
- (r) Data on medical conditions that require Continuous Positive Airway Pressure (CPAP) will be collected during the study. If CPAP is ongoing at the time of informed consent, the medical condition that required CPAP will be captured on the concurrent medical conditions (e)CRF. If CPAP is administered after first dose of study drug, then the medical condition will be captured as an AE.
- (s) If a subject withdraws early, contact IVRS/IWRS to document the ET.
- (t) Subjects to take the first dose of single-blind placebo run-in study medication in-clinic.
- (u) Instruct subjects to withhold their dose of study drug, if applicable so they can be dosed in-clinic. For ABPM subgroup subjects, clinic dosing at 8:00 AM (±2 hours) for Visits 4 and 9.
- (v) Visit 4 is only applied to ABPM subgroup subjects; if the ABPM measurement does not pass the predefined criteria (fails), the subject must continue the current treatment and ABPM should be repeated within 3 days.
- (w) Visit 10 is only applied to ABPM subgroup subjects; if the ABPM measurement does not pass the predefined criteria (fails), the subject must continue the current treatment and ABPM should be repeated within 3 days.

#### 5.0 ANALYSIS ENDPOINTS

## 5.1 Primary Endpoint

The primary endpoint is change from baseline to Week 8 in trough (approximately 24 hours after the previous dose) sitting clinic SBP.

## 5.2 Secondary Endpoints

The secondary endpoints are as follows:

- The change from baseline to Week 8 in trough sitting clinic DBP.
- Percentage of responders at Week 8, as defined by the following:
  - a) Clinic SBP <140 mm Hg and/or reduction of ≥20 mm Hg from baseline.
  - b) Clinic DBP <90 mm Hg and/or reduction of ≥10 mm Hg from baseline.
  - c) a and b.
- Percentage of subjects achieving target blood pressure at Week 8, as defined by the following:
  - a) Clinic SBP <140 mm Hg.
  - b) Clinic DBP < 90 mm Hg.
  - c) Clinic SBP <140 mm Hg and DBP <90 mm Hg.
  - d) Clinic SBP <130 mm Hg.
  - e) Clinic DBP < 80 mm Hg.
  - f) Clinic SBP <130 mm Hg and DBP <80 mm Hg.

## 5.3 Additional Endpoints

Additional endpoints for efficacy are as follows:

## **5.4** Safety Assessments

Safety will be assessed via adverse events (AEs), laboratory tests, 12-lead electrocardiogram (ECG) findings and vital signs (including orthostatic vital signs).

## 6.0 DETERMINATION OF SAMPLE SIZE

Assuming a standard deviation (SD) of 17 mm Hg and a 10% drop-out rate, a sample size of 200 subjects per treatment group (total of 600 subjects) is sufficient to achieve at least 90% power to detect a difference of 6 mm Hg between TAK-491 dose and valsartan by a 2 sample t-test on the mean change from baseline to Week 8 in mean sitting clinic SBP at 0.05 2-sided significance level. This sample size will also provide, for the above assumptions, at least 90% power for demonstrating non-inferiority with a margin of 1.5 mm Hg between TAK-491 and valsartan.

#### 7.0 METHODS OF ANALYSIS AND PRESENTATION

#### 7.1 General Considerations

#### 7.1.1 Statistical Software

Statistical analysis will be performed using the SAS System®, Version 9.2 or higher, on a Windows platform.

## 7.1.2 Summary Statistics and Precision

All tabulations of analysis results will include summaries for the following treatment groups: TAK-491 40 mg once daily (QD), TAK-491 80 mg QD and valsartan 160 mg QD.

Unless otherwise specified, confidence intervals (CIs), statistical tests, and resulting p-values will be reported as 2-sided and will be assessed at the 5% significance level. P-values will be rounded to 3 decimal places prior to assessment of statistical significance.

For continuous variables, descriptive statistics will include the number of subjects (n), mean, SD or standard error (SE) as appropriate, minimum, median, and maximum. In general, the number of decimal places displayed for each statistic will be determined as follows:

- Mean and median: 1 more than the number of decimal places allotted in the raw data received from data management.
- SD and SE: 2 more than the number of decimal places allotted in the raw data.
- Minimum and maximum: equal to the number of decimal places allotted in the raw data.
- CIs will be presented using the same number of decimal places as SD or SE.

Exceptions to the above may be made for derived data. The specific precisions for each derived variables will be included in the derived dataset specifications. For categorical data, frequency counts and percentages will be presented. Percentages will be reported to 1 decimal place.

When applicable, data listings will be accompanied by individual subject data listings sorted by treatment, study centre and subject identifier. The actual day relative to the start of treatment will be determined and included in the listings. All ABPM subjects will be marked in the listings.

Derived analysis datasets will be produced from raw data. This allows for convenient review of the data as well as any necessary supplemental analyses. All data from the raw datasets will be included in the derived datasets. Derived dataset specifications will be developed to include the names and definitions of derived variables in the derived SAS datasets. All analyses and data listings will be performed using the derived datasets.

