## 7.9 Efficacy Analysis

Unless otherwise specified, efficacy analyses will be performed using the FAS and all statistical inference will use a 2-sided 0.05 significance level. Efficacy analyses based on the PPS will also be performed, if appropriate.

The trough sitting clinic SBP/DBP will consist of an average (arithmetic mean) of the non-missing SBP/DBP measurements performed at each visit that satisfy the trough requirements. Post-baseline clinic BP measurements qualify as trough if they are obtained 20-28 hours (inclusive) after the previous study drug dose. Baseline clinic BP measurements are considered trough by default as no double-blind study drug has yet to be taken by subjects.

For the clinic sitting SBP and DBP, missing values will be handled using last observation carried forward (LOCF) methodology. In the LOCF analysis data set, the last observed post-baseline double-blind value will be carried forward and used for all subsequent scheduled time points where data are missing (e.g., the subject has missing data or has dropped out of the study). The efficacy analysis for the response criteria will also be based on the LOCF data set.

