## 7.9.1 Primary Efficacy Endpoint

The primary efficacy endpoint, change from Baseline to Week 8 in trough sitting clinic SBP, will be analyzed using an analysis of covariance (ANCOVA) model, with treatment group as a fixed effect and baseline sitting clinic SBP as a continuous covariate. Estimates of treatment LS mean, differences in LS means between TAK-491 treatment groups and valsartan, p-value and 2-sided 95% CIs for the treatment difference will be determined from the framework of the ANCOVA model. For the primary analysis, the overall type 1 error rate of 0.05 will be controlled using the 4-step sequential test described below.

- Step 1: A test for non-inferiority of TAK-491 80 mg to valsartan 160 mg will be performed using a non-inferiority margin of 1.5 mm Hg. If the upper limit of the 2-sided 95% CI of the treatment difference (TAK-491 valsartan) is not greater than 1.5 then proceed to Step 2.
- Step 2: A test for non-inferiority of TAK-491 40 mg to valsartan 160 mg will be performed using a non-inferiority margin of 1.5 mm Hg. If the upper limit of the 2-sided 95% CI of the treatment difference (TAK-491 valsartan) is not greater than 1.5 then proceed to Step 3.
- Step 3: A test for significant difference between TAK-491 80 mg versus valsartan 160 mg will be performed at the 5% level. If the p-value is not greater than 0.05 then proceed to Step 4.
- Step 4: A test for significant difference between TAK-491 40 mg versus valsartan 160 mg will be performed at the 5% level.

Based on historical data, the observed placebo-corrected treatment effects on change from Baseline in clinic SBP for valsartan 160 mg once daily was -8.6 mm Hg [4]. Therefore, the non-inferiority margin was set conservatively at 1.5 mm Hg, which is less than one-third of the valsartan treatment effect. Accordingly, TAK-491 will be considered non-inferior to valsartan

when the upper limit of the 2-sided 95% CI of the treatment difference (TAK 491- comparator) is  $\leq$ 1.5 mm Hg.

The following sensitivity analyses will be performed for the primary endpoint (change from Baseline in trough sitting clinic SBP at Week 8):

- Conduct the described primary analysis in the PPS to explore the robustness of the primary efficacy result.

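### Rounding p-values to three decimals before judging significance moves the cut-off at Steps 3 and 4 from 0.05 to just under 0.0505, so a pass can disagree with its own 95% CI (minor)

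*SAP*

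**What the plan says.** SAP 7.1.2, in the section on summary statistics and precision, states that "P-values will be rounded to 3 decimal places prior to assessment of statistical significance". The sentence before it says that confidence intervals, "statistical tests, and resulting p-values will be reported as 2-sided and will be assessed at the 5% significance level". SAP 7.9 repeats that "all statistical inference will use a 2-sided 0.05 significance level".

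SAP 7.9.1 sets out a four-step sequence for the primary endpoint and says that "the overall type 1 error rate of 0.05 will be controlled using the 4-step sequential test described below".

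- **Steps 1 and 2** (noninferiority of 80 mg, then 40 mg) are decided by comparing the upper 95% confidence limit with 1.5 mm Hg.
- **Step 3** (difference between 80 mg and valsartan) is decided on the p-value: "If the p-value is not greater than 0.05 then proceed to Step 4".
- **Step 4** reads "A test for significant difference between TAK-491 40 mg versus valsartan 160 mg will be performed at the 5% level".

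The same section says that "95% CIs for the treatment difference will be determined from the framework of the ANCOVA model", so the interval and the p-value for each comparison come from one model.

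Protocol 13.1.3 has the same four steps but no rounding rule. SAP 7.12 records no changes from the protocol's analysis plan.

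**The concern.** The rounding sentence fixes an order of operations: round first, then decide. It is a decision rule placed among formatting conventions. Because the Step 3 rule admits equality with 0.05, rounding before the comparison enlarges the pass region, and nothing in SAP 7.9 or 7.9.1 exempts Steps 3 and 4 from it.

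Two things follow. The nominal level of every p-value-based test becomes 0.0505 where the text says 0.05. And for p-values between 0.0500 and 0.0505, the superiority decision disagrees with the 95% CI reported beside it. At Step 3 that decision also opens Step 4. If a result fell in this window, the sponsor would have to defend a confirmatory claim against its own interval, and the rule could not credibly be changed once the data were unblinded.

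**Working it through.** **Inputs.** SD 17 mm Hg, design difference 6 mm Hg, 200 per arm and 10% dropout (SAP 6.0), giving 200 × 0.90 = 180 evaluable per arm. Noninferiority margin 1.5 mm Hg and two-sided 95% CIs (SAP 7.9.1). The ANCOVA has three treatment groups and one covariate, so df = 3 × 180 − 4 = 536. SD 17 is used as the residual SD because the documents give no other value.

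**1. The plan's own power figure.** SE = 17 × √(2/180) = 1.792 mm Hg. Power = Φ(6/1.792 − 1.960) = Φ(1.388) = 91.7%, or 91.6% by the noncentral t. This agrees with the stated figure of at least 90%.

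**2. What passes.** With conventional half-up rounding:

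| Unrounded p | Rounded p | Not above 0.05? |
|---|---|---|
| 0.0500 | 0.050 | yes |
| 0.0501 | 0.050 | yes |
| 0.0504 | 0.050 | yes |
| 0.05049 | 0.050 | yes |
| 0.0505 | 0.051 | no |

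The working cut-off is therefore p < 0.0505.

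**3. Size on the mm Hg scale.** Critical difference = critical t × SE.

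- At p = 0.05: 1.9644 × 1.792 = 3.520 mm Hg.
- At p = 0.0505: 1.9601 × 1.792 = 3.512 mm Hg.
- Shift: 0.008 mm Hg. With all 200 per arm, the values are 3.339 and 3.331.

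**4. Disagreement with the CI.** An estimate of −3.514 mm Hg gives p = 0.0504, which rounds to 0.050 and passes. Its 95% CI is −3.514 ± 3.520, that is −7.034 to +0.006, which includes zero. At p = 0.05049 the upper limit is +0.0075, close to the largest possible.

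**5. Chance that one test's p-value falls in the window** (noncentral t, both directions counted):

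| True difference | Probability |
|---|---|
| 0 | 0.0005 |
| 6 mm Hg | 0.0007 |
| about 3.5 mm Hg (largest) | 0.0017 |

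Power for 6 mm Hg moves from 91.75% to 91.81%.

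**6. Overall error of the gated sequence.** Simulated with 4 million draws per scenario, a shared valsartan arm, SD 17, 180 per arm and margin 1.5. The entries are the probability of any false claim.

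| Truth | Unrounded | Rounded |
|---|---|---|
| Both doses equal to valsartan | 0.0130 | 0.0131 |
| 80 mg equal, 40 mg highly effective | 0.0251 | 0.0254 |
| 40 mg equal, 80 mg highly effective | 0.0250 | 0.0252 |
| Both doses worse by exactly 1.5 mm Hg | 0.0249 | 0.0249 |

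The rates stay near or below 0.025 because the noninferiority steps block results in the wrong direction. A significant unfavourable difference would need an estimate of at least +3.512, hence an upper limit of at least 3.512 + 3.520 = 7.032, far above 1.5.

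**The case against.** The case for leaving the sentence alone is mainly one of materiality. Rounding would change a Step 3 or Step 4 decision with simulated probability 0.00014 if both doses equal valsartan, 0.0012 if both are at the design difference, and 0.0022 if both are near 3.5 mm Hg. With no true difference only the favourable half of the window matters at these steps, 0.00025 for one test. The rule is written down before unblinding and applies to every comparison, so it leaves no room for later choice. Nor does any sentence make exclusion of zero by the 95% CI a superiority criterion: the SAP yields one decision, and the mismatch is between that decision and a reported interval. The mismatch may not even show in print. If raw blood pressure is recorded in whole mm Hg (an assumption), limits print to two decimals, and an upper limit below 0.005 would appear as 0.00. That covers about 0.005/0.0077 = 65% of the upper-limit range.

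Most of this stands as an argument about size, and it is why the point is graded minor. It does not remove the inconsistency. SAP 7.1.2 says that confidence intervals as well as tests "will be reported as 2-sided and will be assessed at the 5% significance level", yet the p-value rule as written works at 0.0505. Prespecifying a rule that departs from the stated level does not reconcile the two, and rounding in the decision serves no stated purpose.

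**Conclusion.** The point holds, as a minor one. The SAP states a two-sided 0.05 level but applies a cut-off of p < 0.0505 at Steps 3 and 4 and to other p-value-based comparisons, such as the DBP and ABPM analyses. Within that window the decision and the 95% CI disagree, by at most about 0.008 mm Hg at the upper limit. Steps 1 and 2 are unaffected. In the scenarios simulated, the false-claim rate rises by at most about 0.0003 and remains near or below 0.025, so control of the overall type 1 error at 0.05 is not in question.

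These sizes assume a residual SD of 17 mm Hg, 180 evaluable per arm and half-up rounding. A smaller residual SD after baseline adjustment would narrow the window: at an assumed SD of 13, about 0.0077 × 13/17 = 0.006 mm Hg.

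**What to change.** Replace the rounding sentence in SAP 7.1.2 with:

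> Statistical significance will be assessed on unrounded p-values and unrounded confidence limits; p-values will be displayed to 3 decimal places.

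This restores the 0.05 level at Steps 3 and 4 and guarantees agreement with the 95% CI. The mention of confidence limits is a safeguard only: the SAP does not say that limits are rounded before Steps 1 and 2 are decided.

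The cost is one SAP sentence, to be changed before unblinding. Sample size, data collection and Steps 1 and 2 do not change, and power for 6 mm Hg falls by about 0.06 percentage points (91.81% to 91.75%).
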